Femoral neck fracture is a common fracture type in the elderly, and its high disability and mortality make it a fatal killer to the life and health of the elderly. Surgery is the main treatment of femoral neck fracture in the elderly patients. Traditional femoral neck fracture in elderly patients mostly adopts the posterolateral approach (PLA) hemihip arthroplasty under spinal anesthesia, and the direct anterior approach (DAA) emerging in recent years can also be used as an option for the treatment of femoral neck fracture in elderly patients. However, due to the long learning curve of DAA, the operation is difficult, and whether this operation can be used as an effective way of femoral neck fracture in elderly patients still needs further study.

2. purpose of research

1. Primary objective: To evaluate the clinical efficacy of direct anterior approach (DAA) and posterolateral approach (PLA) hemiarthroplasty in the treatment of femoral neck fractures in elderly patients.
2. Secondary purpose: To provide some reference for the clinical treatment of femoral neck fracture in the elderly.

3. Type and principle of the study design

1. Study design

In a prospective controlled study, patients who underwent femoral neck replacement for femoral neck fracture between February 2023 and 20 August 2024 were randomly divided into DAA and PLA groups according to different surgical methods for a 3-month follow-up to compare the outcomes of the two groups.

4. Case selection

1. Inclusion criteria

① Age over 80 years old; ② confirmed unilateral femoral neck fracture by imaging examination; ③ tolerated surgery and consent to surgery; ④ initial HA; independent walking and complete cognitive function before ⑤ injury.

2. Exclusion criteria

① Bilateral femoral neck fracture; ② patients with pathological fracture; ③ with hip dysplasia and rheumatoid osteoarthritis; ④ with systemic or surgical site local infection or inflammatory reaction; ⑤ with other lower limb fractures or severe injuries to other parts of the body; ⑥ with previous history of hip surgery.

5. observation item

General information: gender, age (age), height (cm), weight (kg), comorbidity, American Association of Anesthesiologists (American Society of Anesthesiologists, ASA) classification.

Fracture related data: fracture side division, fracture Garden classification and anatomical site classification, Pauwels angle (°).

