Main indicators: Harris hip function score and VAS pain score before, 1 week, 1 month and 3 months after surgery.

Laboratory indicators: hemoglobin value (hemoglobin, HB) (g / L), creatine kinase value (creatine kinase, CK) (U / L) before and after surgery, and the difference was recorded and calculated.

Surgical index: operation time (min), intraoperative blood loss (ml), and intraoperative blood transfusion rate (%).

Perioperative complications: Surgery-related complications include periprosthetic fracture, dislocation, surgical site infection and LFCN injury, while systemic complications include lower limb venous thrombosis, pulmonary infection, death, etc.

Other indicators: postoperative length difference of both lower limbs,

postoperative discharge, postoperative transfer to ICU, ICU length of stay (days), total length of stay (days), mortality rate (%).

Six, data security monitoring

The clinical study will develop a corresponding data safety monitoring plan according to the risk size. All adverse events are detailed documented, Properhandled and tracked until properly resolved or stable, Report serious adverse events and unexpected events to the Ethics committee, competent authorities, sponsor and drug regulatory department in time; A cumulative review of all adverse events was performed periodically by the principal investigator, Hold investigator meetings when necessary to assess the risks and benefits of the study; Double-blind tests may be performed for emergency unblinding when necessary, To ensure the subjects safety and rights and interests; Studies greater than the minimum risk will schedule an independent data monitor to monitor the study data, The high-risk study will establish an independent data safety monitoring board to monitor the accumulated safety data and efficacy data, To make recommendations on whether the study continues.

VII. Statistical treatment

Statistical analysis of the data was performed using the IBM SPSS Statistics 27 software. Measurement data are expressed as $x \pm s$, compared by t-test or Mann-Whitney U test according to whether the data conform to the normal distribution; count data are compared by χ^2 test or Fisher exact probability method according to the conditions. A $P < 0.05$ was considered as a statistically significant difference.

VIII. Ethics of clinical research

Clinical research will follow the provisions of the Declaration of Helsinki.

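### Harris and VAS are scored at three postoperative visits, but only two-sample tests and no missing-data rule are planned, so unequal, recovery-related missed visits could tilt the 3-month comparison

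*Combined protocol and SAP*

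**What the plan says.** Section 5 lists the repeated scores: "Main indicators: Harris hip function score and VAS pain score before, 1 week, 1 month and 3 months after surgery". Section 3 describes patients "randomly divided into DAA and PLA groups according to different surgical methods" and followed "for a 3-month follow-up to compare the outcomes of the two groups".

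For measurement data, Section VII says only that they are "compared by t-test or Mann-Whitney U test according to whether the data conform to the normal distribution". The rest of that section covers categorical outcomes ("count data are compared by χ^2 test or Fisher exact probability method according to the conditions") and the 0.05 threshold. The plan has no repeated-measures model, no summary across visits, no use of the preoperative score in the between-arm comparison, no analysis set, no missing-data rule and no sensitivity analysis.

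The inclusion criteria in Section 4 require "Age over 80 years old". Death is recorded as a systemic complication, and "mortality rate" appears among the other indicators, but neither is linked to the Harris or VAS analysis. The total is 43 cases. No SD, target difference, power or dropout rate is given.

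**The concern.** A two-sample test takes one value per patient. With four values per patient and no cross-visit summary defined, the tests have to be run one visit at a time. With no missing-data rule, a patient without a 3-month score is absent from the 3-month test, even when the 1-week and 1-month scores show how that patient was recovering.

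Missed visits by living patients are plausible in this age group and may be related to function. If one approach loses more patients who were recovering slowly, its 3-month Harris mean is too high, or its VAS mean too low, and the comparison tilts towards it. Separate tests also give no direct estimate of whether the arm difference changes between visits.

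**Working it through.** **Inputs from the plan.** 43 patients; scores at 1 week, 1 month and 3 months; two-sample tests; 0.05 level.

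**Assumptions, because the plan gives no figures.** Allocation 22 v 21; two-sided testing; Harris SD 12; 1-to-3-month correlation ρ = 0.7 (0.5 also tried); no true difference; odds of missing the 3-month visit 3.3 times higher per SD lower 1-month score.

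**Scale.** The total of 43 cannot be reproduced from any stated inputs. The difference detectable with 80% power is (1.96 + 0.84) × √(1/22 + 1/21) = 2.80 × 0.305 = 0.85 SD, or 0.85 × 12 ≈ 10 points.

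**Why the tilt arises.** When missingness depends on the 1-month score, the bias of the available-case 3-month difference is ρ × SD × (mean standardised 1-month score of attenders in arm A minus that in arm B). Suppose, as an extreme, that exactly the lowest fraction f of 1-month scores is lost. The attenders' mean is then φ(z_f)/(1 − f). At ρ = 0.7 the shift is 0.348 SD for f = 30% and 0.136 SD for f = 10%. The difference is 0.212 SD × 12 ≈ 2.5 points. Gradual rather than all-or-nothing selection must give less.

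**How the likelihood estimate corrects it.** In each arm, take the observed 3-month mean and add b × (1-month mean of all patients − 1-month mean of 3-month attenders), where b is the pooled within-arm slope of the 3-month on the 1-month score. This is what a repeated-measures model does when patients drop out in sequence.

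**Simulated results, in Harris points** (8,000 trials per row; 5,000 for the two rows with 5 percentage points of imbalance):

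| Missing at 3 months | Available-case bias | Likelihood bias | False positives |
|---|---|---|---|
| 0% v 30% | 2.43 | 0.02 | 8.6% favouring the higher-loss arm |
| 5% v 25% | 1.60 | 0.05 | 5.4%, same direction |
| 10% v 30% | 1.55 | 0.03 | 6.1%, same direction |
| 10% v 15% | 0.46 | not tabulated | 5.8% two-sided |
| 5% v 10% | 0.38 | not tabulated | 4.8% two-sided |
| 15% v 15% | about 0 | about 0 | 2.4%, one direction |

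The nominal rate is 2.5% in one direction and 5% two-sided. Every bias favours the arm with more missing data. In patients, 10% v 30% is roughly 0.10 × 22 ≈ 2 against 0.30 × 21 ≈ 6 missed visits; 5 percentage points is about one patient.

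**Sensitivity to the assumptions.** With steeper selection (log-odds slope 1.5 per SD), 30% v 10% gives 0.105 SD at ρ = 0.5 and 0.149 SD at ρ = 0.7, that is 1.3 and 1.8 points at SD 12. The likelihood estimate stays within 0.01 SD of zero.

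**Precision.** The standard errors are nearly equal, for example 4.09 points for the available-case estimate and 4.04 for the likelihood estimate.

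**If the unseen 3-month score drives the missed visit.** At 10% v 30%, available-case bias is 2.1 to 2.2 points and likelihood bias 1.0 to 1.2 points. About half remains.

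**The case against.** A reader might infer that the plan prescribes deleting patients with missing scores. It does not. Both the visit-wise testing and the loss of non-attenders are inferred from the named tests and from silence on missing data. What stands is that nothing in the plan directs any other handling.

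A reader might also infer that the result will be biased. The documents give no dropout rate, no SD and no reason to expect unequal loss. Bias needs loss that both differs by arm and tracks recovery; equal loss by the same mechanism gave none. Even 1.55 points is 1.55/12 = 0.13 SD, about 0.4 of a standard error and under one sixth of the detectable difference. This is fair and limits the severity.

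It would also be too strong to say that a mixed model cures the problem or adds power. The near-zero likelihood bias comes from simulations in which the observed 1-month score drives missingness, which suits the model. A patient who cannot attend because of their condition at 3 months does not fit that assumption. Three further cautions stand:

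- A model including everyone with a postoperative score can be misread as estimating scores after death.
- It leaves out the collected preoperative score unless that is added.
- It replaces the plan's provision for non-normal data, which matters for a bounded score such as VAS.

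Finally, the plan states no hypothesis about recovery over time, so the arm-by-visit contrast is a by-product and not the main reason to change.

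**Conclusion.** The concern holds in a conditional and moderate form. As written, the plan most naturally leads to available-case comparisons at each visit. These are open to bias when missed visits are unequal between arms and related to earlier recovery. At SD 12 and correlation 0.7 the size is about 1.5 points for 10% v 30% missing, 0.3 to 0.5 points for 5 percentage points of imbalance, and none for equal loss. The SD, correlation, missing rates and selection strength are all assumptions.

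A likelihood analysis of all postoperative visits removes the part explained by observed scores at no material cost in precision, and still about halves the bias when the unseen 3-month score is responsible. That is enough to recommend the change. It does not show that the planned comparison would be invalid. The point covers living patients who miss visits; deaths need separate handling.

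**What to change.** For Harris and for VAS, make one linear mixed model over the three postoperative visits the main analysis, with arm, visit, arm-by-visit and preoperative score and an unstructured covariance. Report the arm difference with 95% CI at each visit.

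Alongside it:

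- Report deaths separately by arm. State that the model describes patients while alive and that its estimates are not scores after death.
- Keep the visit-wise t or Mann-Whitney test as a sensitivity analysis for non-normal scores.
- Add a simple missing-not-at-random sensitivity analysis, for example lowering imputed Harris scores in one arm by stepwise amounts (raising them for VAS), and report the shift at which the conclusion changes.
- Tabulate missed visits by arm and visit, with reasons.

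The cost is a revised Section VII, one mixed-model run per score in the SPSS software already named, and modest extra work for the sensitivity analyses. No extra patients, visits or scores are needed. The downside is reliance on missingness being explained by observed scores, which is a weaker assumption than the available-case tests need.

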A Single Center Prospective Controlled Study of Direct Anterior Approach and Posterior Lateral Approach in the Treatment of Femoral Neck Fractures in Elderly Patients

Team leader unit: Fujian Provincial Hospital

Project leader: [name]

Responsible department: emergency surgery department

Contact number: [name]

Participants: Fujian Provincial Hospital

Study years: February 2023 - August 2024

scenario summary

project name	A single-center prospective controlled study of a direct anterior versus posterolateral approach for femoral neck fractures in very elderly patients
purpose of research	To evaluate the clinical efficacy of a direct anterior approach (DAA) versus posterolateral approach (PLA) hemiarthroplasty for femoral neck fractures in advanced elderly patients.
research design	A prospective controlled study including the patients treated for femoral neck fracture between February 2023 and 20 August 2024 were randomly ized into DAA and PLA groups according to different surgical methods for a 3-month follow-up to compare the outcomes of the two groups. Main observations include Harris hip function score (preoperative, 1 week, January, march), VAS pain score (preoperative, 1 week, January, march), secondary observations include operation time, intraoperative bleeding, blood transfusion rate, HB difference before and after surgery, CK before and after surgery, perioperative complications, postoperative lower limb length difference, postoperative discharge, postoperative ICU occupancy rate, ICU stay and total hospital stay.
Total number of cases	43 Cases
Case	① Age over 80 years old; ② confirmed unilateral femoral neck fracture by imaging examination; ③ tolerated surgery and consent to

selection	
surgery; ④ initial HA; independent walking and complete cognitive function before ⑤ injury.

	
① Bilateral femoral neck fracture; ② patients with pathological fracture; ③ with hip dysplasia and rheumatoid osteoarthritis; ④ with systemic or surgical site local infection or inflammatory reaction; ⑤ with other lower limb fractures or severe injuries to other parts of the body; ⑥ with previous history of hip surgery.

statistical method	
In this study, the statistical analysis was performed using the SPSS 27.0 statistical software.

The study period	February 2023
	August, 2024

1. research background

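### CK is analysed as an untimed, unadjusted before/after difference in freshly fractured patients; the comparison is valid under randomisation but loses precision that baseline adjustment would recover

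*Combined protocol and SAP*

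**What the plan says.** The scenario summary lists CK among the secondary observations, in the phrase "HB difference before and after surgery, CK before and after surgery". There the word difference is attached to haemoglobin only. Section 5, under laboratory indicators, goes further: "creatine kinase value (creatine kinase, CK) (U / L) before and after surgery, and the difference was recorded and calculated". No hour or day is given for either draw, and the number of postoperative draws is not stated. The main indicators do have set times: "Harris hip function score and VAS pain score before, 1 week, 1 month and 3 months after surgery".

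Section 4 requires "confirmed unilateral femoral neck fracture by imaging examination" and sets no limit on the interval from injury to surgery. It excludes patients "with other lower limb fractures or severe injuries to other parts of the body", which removes some other sources of raised CK but not the index fracture or the fall. The fracture data to be collected are "fracture side division, fracture Garden classification and anatomical site classification, Pauwels angle"; time since injury is not among them.

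Section VII has continuous variables "compared by t-test or Mann-Whitney U test according to whether the data conform to the normal distribution". It names no baseline covariate and no transformation. It also does not say which CK quantity is tested. The difference is the only derived quantity in Section 5, so I take it to be the one compared.

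**The concern.** A before/after difference gives the preoperative value a fixed weight of one. In these patients that value is measured after an injury, at an unrecorded interval. Each patient's difference can therefore contain two things besides the effect of surgery: whatever injury-related CK did between the draws, and the point on the postoperative curve at which the later sample happened to be taken. Section VII removes neither, and without recorded times they could not be corrected afterwards.

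At stake is the informativeness of one secondary comparison in a 43-patient study. Noise of this kind makes a real difference in CK between approaches harder to detect. If timing differed by arm, it could also produce an apparent difference where none exists.

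**Working it through.** The plan has no CK figure to reproduce: it gives no CK effect size, SD, correlation or power, and the 43 cases come without a derivation.

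**Step 1. Efficiency of the difference, without CK kinetics.** Inputs: N = 43 (scenario summary), split 21 v 22 (assumed); alpha 0.05 (Section VII), taken as two-sided; rho, the pre/post correlation, unknown and varied. Let s0 and s1 be the pre- and postoperative SDs.

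- Variance of the change score: s0² + s1² − 2·rho·s0·s1. With s0 = s1 = SD this is 2(1 − rho)·SD².
- Variance after baseline adjustment: (1 − rho²)·s1².
- Ratio with equal SDs: 2(1 − rho)/(1 − rho²) = 2/(1 + rho).

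For scale, take an effect of 0.855 SD of postoperative CK, which gives 80% power on postoperative CK alone: sqrt(1/21 + 1/22) = 0.305; 0.855/0.305 = 2.80; 2.80 − 1.96 = 0.84, or 80%. For the other two analyses, divide 2.80 by sqrt(2(1 − rho)) or sqrt(1 − rho²) before subtracting 1.96.

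| rho | Variance ratio, change to adjusted | Power, change | Power, adjusted |
|---|---|---|---|
| 0 | 2.00 | 51% | 80% |
| 0.3 | 1.54 | 66% | 84% |
| 0.5 | 1.33 | 80% | 90% |
| 0.7 | 1.18 | 95% | 97.5% |

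The change score is worse than postoperative CK alone only when rho is below 0.5. With unequal SDs the ratio is 1 + (s0/s1 − rho)²/(1 − rho²). It is never below 1, but equals 1 when s0/s1 = rho, so the loss could be smaller than the table shows. These are large-sample figures that ignore the one degree of freedom spent on the covariate.

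**Step 2. Adding draw time, under assumed kinetics.** The documents give no kinetics, so every input here is an assumption: background CK 60 U/L; injury CK with median 200 U/L, log-SD 0.7 and half-life 36 h; injury-to-preoperative-draw delay 12–96 h; surgical CK with median peak 400 U/L at 24 h and log-SD 0.5, 35% lower in one arm; 5% measurement error; 3000 runs. The assumed surgical curve stands at 53% of peak at 6 h, 82% at 12 h, 100% at 24 h, 74% at 48 h and 41% at 72 h.

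| Analysis | Postoperative draw | Power |
|---|---|---|
| Raw difference, Mann-Whitney | spread over 6–72 h | 57% |
| Log CK adjusted for log baseline | spread over 6–72 h | 62% |
| Raw difference, Mann-Whitney | all at 24 h | 71% |
| Log CK adjusted for log baseline | all at 24 h | 76% |

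**Step 3. Is the planned test biased?** Same model, no true difference between arms:

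- Equal delays, draws spread over 6–72 h: mean between-arm difference about 1 U/L; rejection 4.4%.
- Unequal injury-to-draw delays (48–96 h v 12–60 h), draws spread over 6–72 h: spurious difference about 33 U/L; rejection 8.1%.
- The same unequal delays, all draws at 24 h: raw difference about 22 U/L, rejection 6.2%; adjusted log analysis about 0.001 on the log scale, rejection 4.6%.

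**Step 4. Sensitivity to the size of the surgical release.** A second set of runs used preoperative median 200 U/L with log-SD 1.0, half-life 36 h, release half-life 6 h and planned draws spread over 6–48 h. For median peak releases of 300, 400, 600 and 1000 U/L, power from the plan to the full fix rose from about 46% to 68%, 53% to 69%, 56% to 72% and 68% to 74%. The gain falls from about 22 points to about 6.

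**The case against.** The strongest reply is that nothing here invalidates the planned test. If allocation is random and timing similar, injury CK and its clearance are equal in expectation in the two arms and cancel in the comparison. Step 3 bears this out, and a separate null run with draws spread over 6–48 h rejected 4.3%. That stands: a stable resting baseline is not needed for a valid between-arm comparison of differences. Subtraction can even help. In the Step 4 runs the planned difference did better than unadjusted postoperative CK (for example 53% v 41%).

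It also stands that CK is one secondary value, that haemoglobin shares the untimed wording, and that no passage says delays or draw times differ by arm. Section 3 describes allocation as random and, in the same sentence, as following the surgical method. That leaves balance less than assured, but it is a separate issue bearing on every endpoint.

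A reader might infer more than the text supports:

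- That there is one postoperative sample. The number is not stated.
- That injury CK is already falling at the preoperative draw. The injury-to-draw interval is not given, so CK could be rising, at its peak or falling.
- That CK is there to measure muscle damage from the approach. This is a natural inference, but the plan does not say so.

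What the reply does not remove is the precision loss, or the absence of the times needed to check for imbalance.

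**Conclusion.** The point holds as one of precision and incomplete specification. CK is an untimed before/after difference, compared without adjustment, in patients whose preoperative value may already reflect injury. With equal SDs the change score has 1.18 to 2.00 times the variance of the adjusted analysis for rho from 0.7 down to 0. That range depends on the unknown rho and on the equal-SD assumption. The power figures from Step 2 onward depend on assumed kinetics and release size and should be read for direction only.

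Bias is conditional: it requires injury-to-draw or surgery-to-draw time to differ by arm. It would be too strong to conclude that the CK result can neither support nor refute a difference between approaches. The planned analysis kept 46–68% power in these runs, and the full fix itself stayed below 80%. The main conclusions on Harris and VAS are unaffected.

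**What to change.** In Section VII, replace the test on the CK difference with a regression of log postoperative CK on group and log preoperative CK, reported as a ratio of geometric means with a 95% confidence interval.

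In Section 5, set one postoperative CK draw time common to both arms, using the sample already planned, and state which draw enters the analysis if there are several. Record the actual surgery-to-draw and injury-to-draw times, and add them as covariates in a sensitivity analysis.

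The cost is wording in two sections, two recorded times per patient and one regression in SPSS. There is no extra sample or visit. The downsides are small: the result is a ratio instead of a difference in U/L, and some draws will fall outside the window. For samples already taken, the adjusted analysis still applies, and draw times can be added where laboratory records hold them.

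### Two main scores at three postoperative visits have no ranking and no multiplicity rule, and the preoperative scores have no stated role in estimating the effect

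*Combined protocol and SAP*

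**What the plan says.** Section 5 (observation item) sets the main outcomes: "Main indicators: Harris hip function score and VAS pain score before, 1 week, 1 month and 3 months after surgery". The scenario summary lists the same two scores and times. Neither place ranks the scores or the visits. Three months appears in section 3 only as the length of follow-up.

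Section VII (Statistical treatment) has one rule for continuous data. They are summarised by mean and SD and "compared by t-test or Mann-Whitney U test according to whether the data conform to the normal distribution". A P-value below 0.05 "was considered as a statistically significant difference". The section mentions no covariate, change score, repeated-measures model, confidence interval or multiplicity rule.

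The one place where a preoperative value enters a derived quantity is the laboratory paragraph of section 5, where HB and CK are taken "before and after surgery, and the difference was recorded and calculated". Nothing similar is written for Harris or VAS. The total is 43 cases, with no derivation.

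**The concern.** There are two separate gaps.

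The first is ranking. With two scores and three postoperative visits all called main, a result below 0.05 on any of them could be reported as a positive finding on a main indicator. The error rate that matters to the reader is then that of the set, not the 5% of a single test.

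The second is precision. With 43 patients the interval for a difference between approaches will be wide. A preoperative measurement of each main score will be in the dataset, yet the plan does not use it to sharpen the postoperative comparison. Section VII also lets the choice of test follow the data, so P-values at different visits may come from different tests, and it plans no CI for the difference.

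**Working it through.** **Inputs from the documents.** 43 patients (scenario summary); two scores and three postoperative visits (section 5); alpha 0.05 (section VII). The plan gives no effect size, SD, power or dropout, so there is no planned figure to reproduce.

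**Assumptions.** Split 21 vs 22; two-sided tests; all 43 patients measured at the main visit; r, the correlation between the preoperative and main-visit score, shown over 0 to 0.3; correlations among the six test statistics from 0.3 to 0.8.

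**1. Number of tests.** 2 scores × 3 postoperative visits = 6. This is inferred from the general rule; the plan does not state the count.

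**2. Chance of at least one P < 0.05 when no difference exists.**
- Six independent tests: 1 − 0.95^6 = 26.5%.
- Six tests, one common correlation, by simulation: 24% at 0.3, 21% at 0.5, 16% at 0.7, 14% at 0.8.
- Six tests, between-visit correlation 0.3–0.7 and between-outcome correlation 0.3–0.5, by simulation of t-tests: 18.8–24.7%. The top of this range occurs when cross-score correlations at different visits are weaker than those at the same visit.
- Two tests at one visit, 0.05 each: 1 − 0.95² = 9.75% if independent; 8.9–9.6% with between-outcome correlation 0.3–0.5.
- Two tests at one visit, 0.025 each: 1 − 0.975² = 4.9% if independent; 4.5–5.0% simulated.
- One test: 5%.

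The same t-test simulation gave 4.9–5.1% per test, so no single planned test is at fault.

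**3. Precision without adjustment.** Half-width of the 95% CI = t(0.975, 41) × √(1/21 + 1/22) = 2.0195 × 0.3051 = 0.616 SD.

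**4. Precision with ANCOVA on the preoperative score.** Half-width = t(0.975, 40) × √[(1/21 + 1/22)(1 − r²)(1 + 1/39)]. The last factor is the small-sample cost of one covariate with 43 patients. Power is from the noncentral t at an illustrative difference of 0.6 SD.

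| | Half-width (SD) | Power at 0.6 SD |
|---|---|---|
| Unadjusted | 0.616 | 48.4% |
| r = 0 | 0.624 | 47.4% |
| r = 0.1 | 0.621 | 47.8% |
| r = 0.2 | 0.612 | 49.0% |
| r = 0.3 | 0.596 | 51.1% |

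The largest power loss at r = 0 over other differences is 1.15 points, at 0.75 SD.

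**5. Break-even.** On variance, (1 − r²)(40/39) = 1 gives r² = 1/40, so r = 0.158. On half-width, which also loses one degree of freedom, r = 0.163.

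**6. Fewer completers.** With 19 vs 20 measured, the half-width is 0.649 SD unadjusted and 0.629 SD at r = 0.3. The picture is the same.

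**7. Change score instead of ANCOVA.** With equal SDs the variance factor is 2(1 − r). At r = 0.3 this is 1.40, against 0.933 for ANCOVA and 1 unadjusted. A change score loses precision whenever r is below 0.5.

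**The case against.** The best case for the plan is that an unadjusted comparison is valid under randomisation, that preferring ANCOVA is good practice and not the repair of an error, and that its benefit rests wholly on an r the documents do not give. That stands. The preoperative score is taken after the fracture, and eligibility (over 80, "independent walking and complete cognitive function before" injury) narrows the range of patients. Both could make r small, and below about 0.16 there is no gain. Much larger gains follow at r of 0.5 or 0.6, but nothing in the documents supports such values.

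Several stronger readings are tempting and should be resisted:
- *The preoperative scores are not used at all.* The general rule in section VII would cover them, so a between-group comparison at baseline can be read into the plan. What is missing is a stated role in estimating the postoperative effect.
- *The normality switch leaves the reader without an effect estimate.* Section VII plans means and SDs for continuous data whichever test is chosen, so a mean difference can be derived. What is not planned is its CI. No inflation of type I error is claimed for the switch.
- *Three months is the intended main visit.* The documents give it only as the follow-up length. Choosing it is a suggestion.
- *The error rate is at least 19%.* That lower figure depends on moderate correlations; at 0.8 throughout it is about 14%.

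A last objection is timing. The stated study period ended in August 2024, so outcomes may already have been seen. The documents do not say. This limits the status of an adjusted result but does not remove the gap.

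**Conclusion.** The point holds as an improvement worth considering. It does not show that the planned tests are wrong.

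The firmer part is the missing ranking: about a 14–25% chance of at least one false positive across six main tests, against about 5% with one test or two at 0.025. That range assumes all six are run and correlations of 0.3–0.8. It does not depend on r.

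The weaker part is baseline adjustment. Its cost is bounded at about 1 point of power. Its benefit is unknown: none near r = 0.16, and at r = 0.3 a half-width of 0.596 in place of 0.616 SD, about 3% narrower.

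All the error rates presuppose real randomisation. Section 3 describes patients as "randomly divided into DAA and PLA groups according to different surgical methods for a 3-month follow-up", which is ambiguous. If allocation was not random, even the 5% for a single test is not assured, and adjusting for one measured score would not restore it.

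**What to change.** Before outcomes are examined by group, add to section VII:

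1. One main visit, for example 3 months as the end of follow-up, with the other visits labelled supportive.
2. Either one score named as primary, or both tested at 0.025 at that visit.
3. For each main score, the between-group mean difference with its 95% CI from ANCOVA adjusted for that score's preoperative value. Do not use a change score. Keep Mann-Whitney as a sensitivity analysis, not as a switch driven by the data, and check residuals for floor and ceiling effects.
4. A sentence on how Harris and VAS are handled after death, because section 5 lists mortality among the outcomes ("ICU length of stay (days), total length of stay (days), mortality rate").

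If outcomes have already been examined, report the adjusted result as post hoc.

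The change needs no new data, and ANCOVA runs in the named software, SPSS 27. The statistical cost is one degree of freedom. Group means and SDs are already planned, so the added reporting is the adjusted difference and its CI. The real decisions are which visit and score to put first and how to treat deaths.
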